8.2.1. Primary Outcome

The primary outcome will be the incidence of malaria, defined as the number of incident episodes per time at risk. Incident cases will include all treatments for malaria not preceded by another treatment in the previous 14 days. Time at risk will begin at birth and will end when study participants reaches 24 months of age, when the intervention will be stopped, or early study termination (if prior to 24 months of age).

8.2.2. Secondary Outcomes

Secondary outcomes are summarized in Table 8 below.

Table 8. Secondary outcomes

Secondary outcome	Definition
Incidence of complicated malaria	Any treatment for malaria meeting criteria for severe malaria or danger signs
Incidence of hospital admissions	Admission to the pediatric ward for any cause
Incidence of adverse event	Adverse events stratified by type, severity score and relationship to study drugs
Prevalence of anemia	Proportion of routine hemoglobin measurements < 10 g/dL & < 8 g/dL
Prevalence of asymptomatic parasitemia	Proportion of routine samples (PCR or blood smears) positive for asexual parasites.
Prevalence of gametocytemia	Proportion of routine blood smears positive for gametocytes.

8.2.3. Analyses

An intention-to-treat approach to all analyses will be used, including all infants born to mothers assigned to receive IPTp with 3 dose DP or monthly DP and including all follow-up time until the

study participants reach 24 months of age or early study termination regardless of whether the intervention was stopped due to an adverse event.

Primary analysis. We will compare the incidence of malaria using Poisson or negative binomial regression models as described in section 9.1.3. In necessary, multivariate analyses will be performed to adjust for potential confounders and effect modifiers.

Secondary analyses. We will compare the incidence of complicated malaria, hospitalizations, and adverse events using Poisson or negative binomial regression models as described in section 9.1.3. We will compare the prevalence of anemia, asymptomatic parasitemia, and gametocytemia using generalized estimating equations with adjustments for repeated measures in the same study participant. In necessary, multivariate analyses will be performed to adjust for potential confounders and effect modifiers.

8.3. Hypothesis 3

We will test the hypotheses that A) infants born to mothers randomized to receive IPTp with 3 dose DP or monthly DP will have a lower incidence of malaria during the first 24 months of life compared to infants born to mothers who were randomized to receive IPTp with 3 doses of SP, and, B) infants randomized to receive monthly DP between 2-24 months of age will have a lower incidence of malaria between 24-36 months of age after the intervention is stopped compared to infants randomized q 3 monthly DP between 2-24 months of age. For hypothesis 3A, we will only include infants randomized to receive q 3 monthly DP during infancy. For hypothesis 3B, we will also explore for interaction with the intervention given during pregnancy.

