5. STUDY TREATMENT

5.1. Treatment Group Assignments

There will be 5 treatment arms which include both the intervention for the woman during pregnancy and her unborn child(ren) during infancy (Table 3). Non-singleton births from the same mother will be assigned to the same intervention. We will use a 2:1:1:1:1 randomization scheme targeting 100, 50, 50, 50, 50 pregnant women in treatment arms A-E respectively. A randomization list will be computer generated by a member of the project who will not be directly involved in the conduct of the study. The randomization list will include consecutive treatment numbers with corresponding random treatment assignments. Randomized codes will correspond to the 5 treatment groups using permuted variable sized blocks of 6 and 12 (to account for treatment group A being represented twice as often as the other 4 treatment groups). Sealed copies of the original randomization list and documentation of the procedure used to generate the lists will be stored in the project administrative offices in San Francisco and Kampala. Prior to the onset of the study, a set of sequentially numbered, opaque, sealed envelopes will be prepared. Each envelope will be marked on the outside with the treatment allocation number. The inside of the envelope will contain a piece of paper with the treatment allocation number and treatment group assignment along with a piece of carbon paper.

Table 3. Treatment arms with assignment of study drugs during pregnancy and infancy

Phase of intervention	Treatment arm				
	A	B	C	D	E
During pregnancy	3 dose SP	3 dose DP	3 dose DP	Monthly DP	Monthly DP
During infancy	3 monthly DP	3 monthly DP	Monthly DP	3 monthly DP	Monthly DP

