We will test the hypothesis that infants randomized to receive monthly DP between 2-24 months of age will have a lower incidence of malaria during the first 24 months of life compared to infants randomized to receive q 3 monthly DP. Secondary outcomes will include the incidence of complicated malaria, hospitalizations, adverse events, and the prevalence of anemia, asymptomatic parasitemia, and gametocytemia. This hypothesis will be limited to only infants born to mothers assigned to receive IPTp with 3 dose DP or monthly DP to ensure an equal balance of this prior phase of the interventions.

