8.3.3. Analyses

An intention-to-treat approach to all analyses will be used. For hypothesis 3A, we will only include infants randomized to receive q 3 monthly DP during infancy. For hypothesis 3B, we will include all infants that reach 24 months of age. We will compare the incidence of malaria and the incidence of complicated malaria using Poisson or negative binomial regression models as described in section 9.1.3. For hypothesis 3B, we will also explore for interaction with the intervention given during pregnancy.

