Assigned treatment arms in pregnant women	3 doses of SP	3 doses of DP		monthly DP	
Estimated number of pregnant women enrolled	100	100		100	
Estimated number with placental outcomes	90	90		90	
Assigned treatment arms in infants	q 3 monthly DP	q 3 monthly DP	monthly DP	q 3 monthly DP	monthly DP
Estimated number of infants enrolled	90	45	45	45	45
Estimated number of infants reaching 24 months of age	81	41	41	41	41

Table 10. Minimum relative differences in outcomes detectable given estimated effective sample sizes

Hypothesis	Analysis population	Control group and estimated sample size	Comparison group and estimated sample size	Estimated outcome measure in control group	Minimum relative difference detectable*
1	Pregnant women with placental malaria measured at birth	3 dose SP (n=90)	3 dose DP or monthly DP (n=90 each)	Prevalence of placental malaria = 62%	33%
		3 dose DP (n=90)	monthly DP (n=90)	Prevalence of placental malaria = 20-50%	41-70%
2	Infants 0-24 months of age born to mothers assigned to receive IPTp with 3 dose DP or monthly DP	Infants assigned q 3 monthly DP (n=90)	Infants assigned monthly DP (n=90)	Incidence of malaria = 3-5 episode PPY	18-23%
3	Infants 0-24 months of age randomized to q 3 monthly DP	Infants of mothers assigned 3 dose SP (n=90)	Infants of mothers assigned 3 dose DP or monthly DP (n=45 each)	Incidence of malaria = 3-5 episodes PPY	22-28%
	Infants 24-36 months of age after chemoprevention stopped	Infants assigned q 3 monthly DP (n=162)	Infants assigned monthly DP (n=81)	Incidence of malaria = 3-5 episodes PPY	16-21%

* Relative difference = (estimated outcome in control arm – estimated outcome in the comparison arm) / estimated outcome on the control arm (two-sided alpha = 0.05, power = 80%).

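### The Hypothesis 2 primary model does not include the maternal DP arm that the allocation crosses with infant regimen; this costs a little precision and causes no bias (minor)

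*Protocol*

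**What the plan says.** Protocol Section 5.1 sets the allocation: "We will use a 2:1:1:1:1 randomization scheme targeting 100, 50, 50, 50, 50 pregnant women in treatment arms A-E respectively". Table 3 shows that arms B-E cross maternal regimen (3 dose or monthly DP) with infant regimen (3 monthly or monthly DP). The method is permuted blocks: "Randomized codes will correspond to the 5 treatment groups using permuted variable sized blocks of 6 and 12". A full block of 6 therefore holds two women in arm A and one in each of B, C, D and E.

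Section 8.2 restricts Hypothesis 2 to infants of mothers in the DP arms, "to ensure an equal balance of this prior phase of the interventions". For the primary analysis Section 8.2.3 says "We will compare the incidence of malaria using Poisson or negative binomial regression models as described in section 9.1.3". The protocol has no Section 9.1.3; the model text is in Section 8.1.3, which names no covariate either. The next sentence of 8.2.3 allows multivariate analysis, if needed, for possible confounders and effect modifiers, without naming the maternal arm. For Hypothesis 3B, Section 8.3.3 is more specific: "For hypothesis 3B, we will also explore for interaction with the intervention given during pregnancy".

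**The concern.** The design goes out of its way to balance maternal DP regimen across infant regimens, but the Hypothesis 2 model does not use that balance. Section 8.1.3 shows how the need to adjust is judged for Hypothesis 1: by looking for differences between arms in potential confounders. A factor balanced by allocation will usually show no such difference, so the same reasoning in 8.2.3 would leave it out.

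Balance removes bias. It does not remove from the residual any difference in infant malaria between the two maternal arms. A model that estimates overdispersion counts that difference as noise, although the allocation has already equalised it between infant regimens. At stake is some precision in a primary comparison. The conditional rule also leaves the choice of whether the maternal arm enters that model open until the data are in.

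**Working it through.** **1. The plan's own figure.** Table 10 gives a detectable difference of 18-23% for 90 vs 90 infants at 3-5 episodes per person-year (PPY), two-sided alpha 0.05, power 80%. With Poisson variance,

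|ln RR| = (1.960 + 0.842) x sqrt[1/(n0 λ t) + 1/(n1 λ RR t)].

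With t = 1 person-year per infant and λ = 3, RR = 0.772: 2.802 x sqrt(1/270 + 1/208.5) = 0.258 = |ln 0.772|, a difference of 22.8%. At λ = 5 it is 17.9%. The figure reproduces with one person-year per infant, no overdispersion and no maternal term. (Over the stated 0-24 months, at about 1.9 person-years, the formula gives 16.8% and 13.1%; that is a separate matter.)

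**2. Overdispersion from the site's prior trial (Section 1.2, Tables 1 and 2).** Reading the excess over Poisson variance as negative binomial with parameter k:

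- 6-24 months: efficacy interval 45-67%, so SE = ln(0.55/0.33)/3.92 = 0.130. Poisson variance = 1/366 + 1/760 = 0.00405. Ratio = 0.0170/0.00405 = 4.2. With about 98 children per arm (393/4), k = (0.0170 - 0.00405)/(2/98) = 0.63.
- 24-36 months: interval 0.79-1.25, so SE = ln(1.25/0.79)/3.92 = 0.117. Poisson variance = 1/659 + 1/670 = 0.00301. Ratio = 4.6. With about 88 per arm (352/4), k = 0.47.

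I use k = 0.5 and 0.63, with 0.2 as a lower case.

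**3. Standard error with and without the maternal arm.** Let m = 1.9λ be the mean episodes per infant, r the assumed infant rate ratio between the two maternal DP arms, and c = [(1-r)/(1+r)]². The SE of the log rate ratio is sqrt(2V/90), where

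- without the maternal arm: V = 1/m + k + c(1+k)
- with it: V = 2/(1/v1 + 1/v2), where v_i = 1/m_i + k, m1 = 2m/(1+r), m2 = 2mr/(1+r).

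Example with λ = 3 (m = 5.7), k = 0.5:

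- r = 0.8, c = 0.0123: V = 0.694 without and 0.677 with; sqrt(0.677/0.694) = 0.988, 1.2% narrower.
- r = 0.5, c = 0.111: V = 0.842 without and 0.691 with; sqrt(0.691/0.842) = 0.906, 9.4% narrower.

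Narrowing of the interval (log scale) over 3-5 PPY:

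| r | k = 0.5-0.63 | k = 0.2 |
|---|---|---|
| 0.9 | 0.3% | 0.4-0.5% |
| 0.8 | 1.1-1.4% | about 2% |
| 0.7 | 2.7-3.4% | 4-5% |
| 0.5 | 9-11% | 13-16% |

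**4. How much of this is overstatement.** With equal cells, the true spread of the unadjusted estimate has V = 1/m + k(1+c), so the reported V is too large by exactly c. At 4 PPY (m = 7.6) and k = 0.5 the SE is overstated as follows:

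- r = 0.8: sqrt(0.650/0.638), 1.0%
- r = 0.7: sqrt(0.678/0.647), 2.4%
- r = 0.5: sqrt(0.798/0.687), 7.8%

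With k = 0.63 the figures are 0.8%, 2.0% and 6.5%.

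**5. Simulation.** Four cells of 45, 1.9 person-years each, 4 PPY, 600 runs per setting, negative binomial fits:

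| k | r | Mean SE without | Mean SE with | Coverage without | Coverage with |
|---|---|---|---|---|---|
| 0.5 | 0.8 | 0.1193 | 0.1179 | 93.7% | 93.0% |
| 0.5 | 0.5 | 0.1283 | 0.1182 | 94.2% | 92.8% |
| 0.2 | 0.8 | 0.0872 | 0.0854 | 94.0% | 93.7% |
| 0.2 | 0.5 | 0.1000 | 0.0864 | 96.7% | 94.7% |

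Coverage carries a simulation error of about sqrt(0.95 x 0.05/600) = 0.9 points. Unadjusted coverage is above nominal only in the last row. The model-based Poisson SE does not move (0.0543 both ways at r = 0.8, 0.0542 both ways at r = 0.5).

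**The case against.** The case against is substantial.

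- **Validity.** An unadjusted comparison of randomised groups is valid. This stands: the omission does not bias the infant comparison.
- **Place.** Covariate lists often sit in a statistical analysis plan, and none is shown. This stands in part. The protocol does more than stay silent: it states a conditional rule that suits a factor balanced by allocation poorly.
- **Effect modification.** A reader might infer that Hypothesis 2 has no check of effect modification. The documents do not support that, because 8.2.3 provides for effect modifiers in general terms. It only does not name the maternal arm.
- **Comparison with 3B.** A reader might also see an inconsistency with 3B, which names the interaction. But 3B takes all infants who reach 24 months (162 vs 81 in Table 10). That includes arm A, whose mothers received SP and whose infants all receive 3 monthly DP. Maternal and infant regimens are unbalanced there, a specific reason to name the pregnancy intervention. Hypothesis 2 handles this by leaving arm A out.
- **Size of the maternal effect.** Hypothesis 3A contrasts DP with SP, so it does not supply a ratio between the two DP regimens. Every r used here is an assumption.
- **Variance.** Assuming Poisson variation between infants makes the effect look larger, but the prior trial points to 4.2-4.6 times that variance, which dilutes it.

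**Conclusion.** The point holds as a minor one. The Hypothesis 2 model leaves out a randomised factor that the allocation crosses 1:1 with infant regimen, and the adjustment rule will normally not bring it in. If the fitted model estimates overdispersion, the standard error is slightly too large: about 1-3% for a maternal rate ratio of 0.7-0.8 and roughly 7-11% at 0.5. The upper values count the whole narrowing when the factor is added; the lower ones count only the overstatement against the true spread.

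This rests on k of about 0.5-0.63, 45 infants per cell, 1.9 person-years each and an assumed ratio. Losses and multiple births would disturb the exact balance a little. It would be wrong to conclude that the Hypothesis 2 interval is too wide or the test conservative in general: a model-based Poisson fit shows no change, and simulated coverage exceeded nominal in only one of four settings. Table 10 is not affected, since its figure carries no maternal term and no overdispersion.

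**What to change.** In Section 8.2.3, state that the primary Hypothesis 2 model includes infant regimen and maternal IPTp arm (3 dose DP vs monthly DP) as fixed factors, whichever count model is used. This costs one sentence and one degree of freedom, needs no new data, and settles before unblinding whether the maternal arm enters. Optionally, name the maternal-by-infant interaction as an exploratory check in place of the general reference to effect modifiers. When the sentence is edited, correct the pointer from 9.1.3 to 8.1.3.

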8.3.1. Primary Outcome

The primary outcome will be the incidence of malaria, defined as the number of incident episodes per time at risk. Incident cases will include all treatments for malaria not preceded by another treatment in the previous 14 days. For hypothesis 3A, time at risk will begin at birth and will end when study participants reaches 24 months of age or early study termination (if prior to 24 months of age). For hypothesis 3B, time at risk will begin at 24 months of age and will end when study participants reaches 36 months of age or early study termination (if between 24-36 months of age).

8.3.2. Secondary Outcomes

The incidence of complicated malaria will be included as a secondary outcome for both hypothesis 3A and 3B.

8.3.3. Analyses

An intention-to-treat approach to all analyses will be used. For hypothesis 3A, we will only include infants randomized to receive q 3 monthly DP during infancy. For hypothesis 3B, we will include all infants that reach 24 months of age. We will compare the incidence of malaria and the incidence of complicated malaria using Poisson or negative binomial regression models as described in section 9.1.3. For hypothesis 3B, we will also explore for interaction with the intervention given during pregnancy.

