3. STUDY DESIGN

This will be a double-blinded randomized controlled phase III trial of 300 HIV uninfected pregnant women and the children born to them. The study interventions will be divided into two phases. In the first phase, HIV uninfected women at 12-20 weeks gestation will be randomized in equal proportions to one of three IPTp treatment arms: 1) 3 doses of SP, 2) 3 doses of DP, or 3) monthly DP. All three interventions arms will have either SP or DP placebo to ensure adequate blinding is achieved in the study as outlined in appendix D. Follow-up for the pregnant women will end approximately 6 weeks after giving birth. In the second phase of the study, all children born to mothers enrolled in the study will be followed from birth until they reach 36 months of age. Children born to mothers randomized to receive 3 doses of SP during

pregnancy will receive DP every 3 months between 2-24 months of age. Children born to mothers randomized to receive 3 doses of DP or monthly DP during pregnancy will receive either DP every 3 months or monthly DP between 2-24 months of age. To ensure adequate blinding, children who will receive DP every 3 months will be given DP placebo during the months they will not be taking DP. Children will then be followed an additional year between 24-36 months of age following the interventions.

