Appendix D. Administration of study drugs and placebos

Timing of administration of study drugs during pregnancy

Weeks of gestation	3 dose SP (treatment arm A)	3 dose DP (treatment arms B+C)	Monthly DP (treatment arms D+E)
16	DP placebo + SP placebo	DP placebo + SP placebo	DP + SP placebo
20	SP + DP placebo	DP + SP placebo	DP + SP placebo
24	DP placebo + SP placebo	DP placebo + SP placebo	DP + SP placebo
28	SP + DP placebo	DP + SP placebo	DP + SP placebo
32	DP placebo + SP placebo	DP placebo + SP placebo	DP + SP placebo
36	SP + DP placebo	DP + SP placebo	DP + SP placebo
40	DP placebo + SP placebo	DP placebo + SP placebo	DP + SP placebo

Timing of administration of study drugs during infancy

Weeks of age	3 monthly DP (treatment arms A+B+D)	Monthly DP (treatment arms C+E)
8	DP	DP
12	DP placebo	DP
16	DP placebo	DP
20	DP	DP
24	DP placebo	DP
28	DP placebo	DP
32	DP	DP
36	DP placebo	DP
40	DP placebo	DP
44	DP	DP
48	DP placebo	DP
52	DP placebo	DP
56	DP	DP
60	DP placebo	DP
64	DP placebo	DP
68	DP	DP
72	DP placebo	DP
76	DP placebo	DP
80	DP	DP
84	DP placebo	DP
88	DP placebo	DP
92	DP	DP
96	DP placebo	DP
100	DP placebo	DP
104	DP	DP

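### Hypothesis 3B pools all infants, but infants of SP mothers occur only in the q3-monthly group, so the infant comparison is confounded with the maternal regimen

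*Protocol*

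**What the plan says.** Section 5.1 randomises mothers and their unborn children together to five arms: "We will use a 2:1:1:1:1 randomization scheme targeting 100, 50, 50, 50, 50 pregnant women in treatment arms A-E respectively". By Table 3 and Appendix D, q3-monthly infant DP is given in arms A, B and D, and monthly infant DP only in arms C and E. Arm A is the whole SP group. Section 3 says of children of SP mothers that, after SP in "pregnancy will receive DP every 3 months between 2-24 months of age", with no alternative regimen offered.

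Section 8.2 compares the two infant regimens at 0-24 months and restricts the population: "This hypothesis will be limited to only infants born to mothers assigned to receive IPTp with 3 dose DP or monthly DP". The stated reason is "to ensure an equal balance of this prior phase of the interventions".

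Section 8.3.3 compares the same two regimens at 24-36 months without that restriction: "For hypothesis 3B, we will include all infants that reach 24 months of age". The 3B row of Table 10 confirms the pooling. Its control group reads "Infants assigned q 3 monthly DP (n=162", against 81 on monthly DP. The only mention of the mother's regimen in 3B is an exploratory interaction. For the models, section 8.3.3 refers to a section 9.1.3 (apparently 8.1.3), which allows multivariate adjustment if necessary.

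**The concern.** The two infant groups differ by design in what their mothers received. Randomisation cannot even this out, because no arm combines SP in pregnancy with monthly DP in infancy. If the mother's regimen still affects the child's malaria rate in the third year of life, the 3B estimate mixes that effect with the effect of infant dosing.

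The protocol has reason to take this seriously. Hypothesis 3A is that maternal DP lowers infant malaria relative to SP, and section 1.3 presents the two-phase design as a way to test the pregnancy and infancy effects independently. As written, 3B does not separate them. It is a primary comparison under hypothesis 3, which section 8.4 names as the main determinant of the sample size.

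**Working it through.** **Composition.** Table 9 expects 81 arm A infants and 41 in each of arms B-E at 24 months. The share with an SP mother is 81/(81+41+41) = 81/163 = 49.7% in the q3-monthly group and 0/82 in the monthly group. Table 10's 162 and 81 differ from these sums only by rounding.

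**Reproducing Table 10.** Inputs: two-sided alpha 0.05, power 80%, control rate λ of 3-5 episodes per person-year, one person-year per child. The detectable relative difference r solves λr / √(λ/n₀ + λ(1−r)/n₁) = 1.96 + 0.84.
- 162 versus 81: r = 16.1% (λ=5) and 20.5% (λ=3). Pooled-variance, log-ratio and square-root versions give 16.3-16.6% and 20.8-21.3%. The stated 16-21% is reproduced.
- 81 versus 81: 18.7% and 23.9%. 82 versus 82: 18.6% and 23.7%.

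The stated figure therefore depends on the arm A infants. With 82 versus 82, power at the stated differences falls from about 79% to 67% (16%, λ=5) and from about 82% to 69% (21%, λ=3).

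**Size of the bias.** Suppose infant dosing has no effect after 24 months, and infants of DP mothers have a rate lower by a fraction d than infants of SP mothers, whose rate is λ. The q3-monthly mean is λ(1−d/2) and the monthly mean is λ(1−d). The apparent reduction is 1 − (1−d)/(1−d/2) = d/(2−d).

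The type I error comes from a Wald test on the log rate ratio, with variance 1/(162·λ(1−d/2)) + 1/(81·λ(1−d)), plus k(1/162 + 1/81) if counts are overdispersed.

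Example with d=0.22, λ=5: the means are 4.45 and 3.90, and the log ratio is 0.132. Under Poisson variance the standard error is √(1/720.9 + 1/315.9) = 0.0675, so z = 1.95 and the rejection rate is about 50%. With k=0.48 the variance is 0.00455 + 0.48 × 0.0185 = 0.0134 and the standard error 0.116, so z = 1.14 and the rejection rate is about 21%.

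| Assumed maternal effect at 24-36 months (d) | Spurious reduction | Type I error, Poisson, λ=3-5 | Type I error, k=0.48, λ=3-5 |
|---|---|---|---|
| 0 | 0 | 5% | 5% |
| 10% | 5.3% | 10-14% | 7-8% |
| 22% | 12.4% | 33-50% | 18-21% |
| 28% | 16.3% | 51-72% | 28-33% |

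**Where d and k come from.** The protocol gives no maternal effect at 24-36 months. The 22-28% is borrowed from the 3A row of Table 10, where it is a detectable difference for 0-24 months, so it serves as a worst case. The k is also an assumption, but the prior trial in Table 2 supports it. For prior monthly DP the interval 0.79-1.25 gives a standard error of (ln 1.25 − ln 0.79)/3.92 = 0.117. Its square, 0.0137, less the Poisson part 1/670 + 1/659 = 0.0030, leaves 0.0107. With 352/4 = 88 children per arm, k is about 0.0107 × 88/2 = 0.47.

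**The case against.** The bias needs a maternal effect that outlasts the second birthday, and nothing in the protocol predicts one. Hypothesis 3A stops at 24 months. Section 1.1 says it is unclear whether preventing malaria in pregnancy reduces the child's risk after birth. The only post-intervention data shown, in Table 2, give a rate ratio of 0.99 (0.79-1.25) for prior monthly DP, so no carry-over is visible. These points stand as limits on the size. They do not remove the confounding: Table 2 concerns infant dosing, not maternal dosing, and one cited observational study reports in its title a raised malaria risk over the first 30 months of life after placental malaria.

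The plan also has partial safeguards. An interaction model with maternal main effects would give infant contrasts within the 3-dose DP and monthly DP mothers, free of the SP imbalance. Adjustment is allowed if necessary. Overdispersion is to be tested and variances adjusted, so the k=0.48 column is probably closer to practice than the Poisson one. But the interaction is exploratory and has an empty cell for SP mothers with monthly infant DP. The adjustment is optional and does not name maternal arm. Neither makes the primary test clean. With maternal arm in the model, arm A contributes nothing to the infant contrast, and the 16-21% no longer applies.

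A reader might infer that the randomisation is broken. It is not. A+B+D versus C+E is a randomised comparison of combined maternal and infant strategies, and B+D versus C+E can be recovered from the same data. What fails is reading the pooled result as the effect of infant dosing alone.

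**Conclusion.** The concern holds as a confounded analysis population for one primary comparison, inconsistent with the protocol's own reasoning for hypothesis 2. The imbalance is certain; the size of the bias is conditional. It is zero if no maternal effect persists past 24 months, modest for a 10% effect, and close to the claimed detectable difference only in the worst case. A reader might take the 12-16% spurious reduction, or the matching false-positive rates, as expected values. The documents do not support that, because 22-28% is neither an anticipated effect nor one stated for 24-36 months. The direction, in favour of monthly DP, likewise assumes that a persisting effect runs as hypothesis 3A proposes. The analyses of hypotheses 1, 2 and 3A are not affected.

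**What to change.** In section 8.3.3, define the primary 3B analysis as arms B+D versus arms C+E among infants reaching 24 months, stratified or adjusted for maternal arm (3-dose DP versus monthly DP). Limit the interaction test to those two maternal groups. Keep the all-infant comparison as secondary at most, described as a comparison of combined strategies.

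Restate the 3B row of Table 10 as about 81 versus 81 (82 versus 82 by the Table 9 sums), with a detectable difference of about 19-24% on the same Poisson basis, and make the matching change in the text of section 8.4.

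The cost is a somewhat less favourable stated detectable difference. Enrolment, randomisation and conduct do not change, and no extra participants are needed.
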